5.6.3.3. Electrocardiogram

Evaluation of the triplicate 12-lead ECGs will be based on the mean value of the triplicate parameters and the abnormalities will be defined on the triplicate means.

The ECG parameters that will be analyzed are heart rate (bpm), PR interval (ms), RR interval (ms), QRS interval (ms), QT interval (ms), and corrected QT (QTc) interval using the following correction methods:

Fridericia's formula: $QTcF$ (msec) = QT (msec) / $(RR$ (msec)/1000) $^{1/3}$; if RR is missing, use QT (msec) * $(HR$ (bpm)/60) $^{1/3}$;

The abnormalities in ECG parameters will be determined according to the criteria specified in the Cardiovascular Safety – Abnormalities Table (see Clinical Protocol Appendix 8, Cardiovascular Safety- Abnormalities Table). Abnormalities on actual values are provided for HR, PR, QRS and QTcF. Additional abnormalities on change from baseline will be provided for QTcF. No abnormalities will be defined for actual uncorrected QT values. Uncorrected QT \geq 500 ms will be flagged and only shown in listings.

An assessment is treatment-emergent if abnormality worsened as compared to the abnormality at baseline; this also includes the shift from abnormally high to abnormally low and vice-versa. Post-reference abnormalities are always treatment-emergent with regard to missing abnormalities at baseline. The abnormally high values (i.e. abnormally high, borderline prolonged, prolonged, pathologically prolonged) versus the abnormally low values are considered equally important. Abnormalities defined on changes from baseline are always treatment-emergent.

For each parameter, a “worst-case” analysis will be performed by using the worst abnormality and time point per participant. Worst-case will be derived within each analysis phase, including unscheduled assessments. In case the same participant has both abnormalities (low and high) for the same test within the same phase, the participant will be counted in the analysis for both abnormality directions (abnormally high and low).

Only data from the vendor ERT will be analyzed. All other ECG data will be listed.

For the time points on which triplicate ECGs apply, a rounded mean value to the next integer per triplet will be calculated per time point before any further handling. This rounded mean value will be used through the entire analysis also in case of 1 or 2 missing values.

ECG records with partial dates (any of day/month/year is missing) will not be used in analysis, except in the listings. The following imputation rules will be applied.

If heart rate (HR) is missing, it will be calculated using RR (if available) and rounded to the integer value (see formula below) before any further handling if applicable.

$$\frac{1000}{RR(ms)} = \frac{HR(bpm)}{60}$$

HR from the vital signs section (i.e. pulse) will not be used in this ECG analysis section. RR values (if available) will only be listed. Recalculated HR values will be flagged.

Descriptive statistics will be calculated for observed values and changes from baseline per parameter (all parameters except for RR) at each scheduled time point.

Shift tables will be provided summarizing the shift in ECG values from baseline over time with respect to abnormality category (low, normal, high) for each parameter by analysis phase.

A cross-tabulation of the worst abnormalities (on actual values) versus baseline per parameter by analysis phase will be presented including also the number of participants per abnormality. A tabulation of number and percentage of the participants who have treatment-emergent worst abnormalities per parameter (i.e. for HR, PR, QRS and QTcF) and analysis phase will also be presented.

A cross-tabulation of the worst change from baseline abnormalities (i.e. for QTcF) versus the baseline category per parameter will be presented by analysis phase.

Frequency tabulations of categorized corrected QT/QTc change from baseline (≤ 30 msec, $>30- \leq 60$ msec, >60 msec) and categorized corrected QT/QTc interval values (≤ 450 msec, $>450- \leq 480$ msec, $>480- \leq 500$ msec, >500 msec) per timepoint will be presented.

Listings including all parameters for participants with at least one treatment-emergent abnormality (on actual values or change from baseline), including all findings (e.g. interpretation, rhythm, or technical findings) for participants with uncorrected QT values ≥ 500 ms will be provided separately.

5.6.3.4. Vital Signs and Body Temperature

The following parameters measurements will be analyzed:

- Supine pulse rate (bpm)
- Supine systolic blood pressure (mmHg)
- Supine diastolic blood pressure (mmHg)
- Body temperature ($^{\circ}\text{C}$)

The abnormalities in vital signs will be determined according to the criteria specified in the Cardiovascular Safety – Abnormalities Table (see Clinical Protocol Appendix 8).

An assessment is treatment-emergent if abnormality worsened as compared to the abnormality at baseline; this also includes the shift from abnormally high to abnormally low and vice-versa. Post-baseline abnormalities are always treatment-emergent with regard to missing abnormalities at baseline. The abnormally high values (i.e. abnormally high, grade 1 or mild, grade 2 or moderate, grade 3 or severe) versus the abnormally low values are considered equally important.

For each parameter, a “worst-case” analysis will be performed by using the worst abnormality and time point per participant. Worst-case will be derived within each analysis phase, including unscheduled assessments. In case the same participant has both abnormalities (low and high) for the same test within the same phase, the participant will be counted in the analysis for both abnormality directions (abnormally high and low).

Vital signs records with partial dates (any of day/month/year is missing) will not be used in the analysis but will be listed.

Descriptive statistics of continuous vital sign parameters and body temperature will be calculated for observed values and changes from baseline at each scheduled time point.

Shift tables will be provided summarizing the shift in vital sign and body temperature values from baseline over time with respect to abnormality criteria (low, normal, high) for each parameter by analysis phase.

A cross-tabulation of the worst abnormalities versus baseline per parameter and analysis phase will be presented including also the number of participants per abnormality, the number of participants with treatment emergent abnormalities per abnormality.

A tabulation of percentage and number of the participants who have treatment-emergent worst abnormalities per parameter and analysis phase will be included.

A listing including all parameters for participants with at least one treatment-emergent abnormality (on actual values or change from baseline) is provided. Additional vital signs assessments corresponding to the rash eCRF pages will be only listed as applicable.

5.6.3.5. Physical and Ophthalmic Examinations

The physical and ophthalmic examination findings and abnormalities will be listed. A listing of participants who experienced a decrease or loss of vision at any timepoint during study will be provided.

5.7. Other Analyses

5.7.1. Pharmacokinetics

Descriptive statistics (n, mean, standard deviation [SD], coefficient of variation [CV], geometric mean, median, minimum, and maximum) will be calculated for the plasma concentrations of JNJ-3989 (JNJ-3976, and JNJ-3924), and, optionally, of NA, PegIFN- α 2a and/or JNJ-6379, and for the derived plasma PK parameters for noncompartmental PK analyses.

For each participant with intensive PK sampling, plasma concentration-time data of JNJ-3976, and JNJ-3924, and, optionally, of NA, PegIFN- α 2a and/or JNJ-6379, will be graphically presented. Similarly, graphs of the mean plasma concentration-time profiles and overlay graphs with combined individual plasma concentration-time profiles will be produced. Plasma PK parameters in participants undergoing intensive PK sampling will be calculated via noncompartmental methods for JNJ-3976, and JNJ-3924, and, optionally, NA, PegIFN- α 2a and/or JNJ-6379. The PK parameters will be C_{max} , C_{24h} , and AUC_{24h} ; other PK parameters may also be calculated. The PK parameters will be subjected to an exploratory graphical analysis, including various transformations, to get a general overview.

To assess the effect of PegIFN- α 2a on JNJ-6379 (as applicable) and JNJ-3989, the PK parameters of JNJ-6379 (as applicable) and JNJ-3989 coadministered with PegIFN- α 2a at Week 20 (or 16) will be compared to those of JNJ-6379 (as applicable) and JNJ-3989 at Week 4 (or 8) as reference. The primary PK parameters are C_{max} and AUC_{24h} on the logarithmic scale. A mixed effects model

will be fitted to log-transformed PK parameters with treatment period as a fixed effect and participant as a random effect.

Special attention will be paid to the plasma concentrations and PK parameters of those participants who discontinued the study for an AE, or who experienced an AE \geq grade 3, or an SAE.

Population PK analysis of plasma concentration-time data of JNJ-6379 (as applicable), JNJ-3976, and JNJ-3924 may be performed using non-linear mixed effects modeling. Data from the current study may be combined with prior information available from Phase 1 and/or 2 studies to support a relevant structural model. Available baseline characteristics (eg, demographics, laboratory variables, genotypes) may be included in the model as necessary. If a population PK analysis is conducted, the results will be presented either in the clinical study report or in a separate report.

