Tenofovir alafenamide is an ester prodrug of the NA tenofovir that is indicated for the treatment of chronic HBV infection in adults and that is characterized by a better safety profile than tenofovir disoproxil. The most common adverse reaction ($\geq 10\%$ of participants) is headache.

The single common toxicity target organ between JNJ-6379, JNJ-3989, and tenofovir disoproxil or TAF is the kidney (see Section 2.2.2.2, Combination of JNJ-3989 or JNJ-6379 With Entecavir, Tenofovir Disoproxil, or Tenofovir Alafenamide).

Clinical data on dual combination treatment of JNJ-6379 and NA are available from the ongoing Phase 2a 56136379HPB2001 study ([IB JNJ-6379 2021](#)). In participants treated with tenofovir disoproxil, C_{trough} concentrations of tenofovir at Week 12 were higher in participants receiving tenofovir disoproxil in combination with JNJ-6379 than in participants receiving tenofovir disoproxil as monotherapy (94.2 [30.0] and 115 [66.0] ng/mL for 75- and 250-mg JNJ-6379, respectively in combination with tenofovir disoproxil, vs 66.8 [37.0] ng/mL as tenofovir disoproxil monotherapy).

Clinical data of triple combination treatment of JNJ-3989, JNJ-6379, and NA are available from the Phase 1/2a AROHBV1001 study (see Section 2.2.3.1, JNJ-3989 and JNJ-6379). Dosing JNJ-6379 with NA for 12 weeks did not show any clinically relevant changes in kidney parameters/glomerular function.

For further information regarding ETV, tenofovir disoproxil, and TAF, refer to the respective currently approved prescribing information.

Overall Assessment of the Combination Therapy

Based on the points listed below, no clinically relevant DDIs and no specific concerns about additive or synergistic toxicities in the kidney are expected when JNJ-6379 or JNJ-3989 are combined with ETV, or tenofovir disoproxil, or TAF:

- Available toxicology data, described in Section 2.2.2.2, Combination of JNJ-3989 or JNJ-6379 With Entecavir, Tenofovir Disoproxil, or Tenofovir Alafenamide.
- In vitro drug transporters.
- Metabolic interaction data.
- Absence of relevant DDIs in the combination toxicity studies up to 3 months with JNJ-6379 and JNJ-3989.
- Absence of synergistic or additive histology findings in the kidney observed in the combination toxicity studies up to 3 months with JNJ-6379 and JNJ-3989.
- Available clinical data with JNJ-6379 (JADE study [56136379HPB2001]) up to 24 weeks treatment on the absence of changes in kidney parameters/glomerular function.

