4.2. Scientific Rationale for Study Design

Addition of PegIFN- α 2a to Treatment Regimen

The combination of the treatment regimen of JNJ-3989 + NA with PegIFN- α 2a is based on 2 different properties of IFN- α : a direct antiviral effect and an immune boosting effect. The direct antiviral activity against HBV replication, and in some cases HBsAg production, was demonstrated for PegIFN- α 2a ([Belloni 2012](#)). In addition, IFN- α is expected to act as immune booster with potential to reactivate NK-cells ([Gill 2016](#)). Addition of short-term PegIFN- α 2a (12 weeks) to the treatment regimen is expected to enhance antiviral activity of JNJ-3989 + NA and may lead to a shorter overall treatment duration (ie, 24 weeks) needed to achieve functional cure.

Study Design Change – Protocol Amendment 3

Based on emerging data from the REEF-1 (73763989HPB2001) and REEF-2 (73763989PAHPB2002) studies, the study design has been adapted in Protocol Amendment 3.

In summary, the data from the REEF-1 and REEF-2 studies suggested that JNJ-6379 has a negative impact on the HBsAg lowering effect of JNJ-3989+NA (see details in Section 2.2.3.1) and that JNJ-6379 in combination with TDF may further contribute to renal tubulo-toxicity (see details in Section 2.3.2.2.2). Together, this led to a conclusion of an unfavorable benefit-risk balance of JNJ-6379 in combination with JNJ-3989+NA, compared to JNJ-3989+NA alone. Therefore, the Sponsor decided to discontinue treatment with JNJ-6379 in all ongoing clinical studies effective immediately and as an urgent safety measure. Participants currently on treatment with JNJ-6379 were contacted and requested to stop taking JNJ-6379, while continuing treatment with NA, JNJ-3989, and PegIFN- α 2a. For newly enrolled participants, JNJ-6379 was taken out of the treatment regimen.

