9.4.4. Other Analyses

Pharmacokinetic Analyses

Descriptive statistics (n, mean, SD, coefficient of variation [CV], geometric mean, median, minimum, and maximum) will be calculated for the plasma concentrations of JNJ-3989 (JNJ-3976, and JNJ-3924) and, optionally, of NA, PegIFN- α 2a and/or JNJ-6379, and for the derived plasma PK parameters for noncompartmental PK analyses.

For each participant with intensive PK sampling, plasma concentration-time data of JNJ-3976 and JNJ-3924, and, optionally, of NA, PegIFN- α 2a and/or JNJ-6379, will be graphically presented. Similarly, graphs of the mean plasma concentration-time profiles and overlay graphs with combined individual plasma concentration-time profiles will be produced. Plasma PK parameters in participants undergoing intensive PK sampling will be calculated via noncompartmental methods for JNJ-3976 and JNJ-3924, and, optionally, NA, PegIFN- α 2a and/or JNJ-6379. The PK parameters will be C_{max} , C_{24h} , and AUC_{24h} ; other PK parameters may also be calculated. The PK parameters will be subjected to an exploratory graphical analysis, including various transformations, to get a general overview.

To assess the effect of PegIFN- α 2a on JNJ-6379 (as applicable) and JNJ-3989, the PK parameters of JNJ-6379 (as applicable) and JNJ-3989 coadministered with PegIFN- α 2a at Week 20 (or 16) will be compared to those of JNJ-6379 (as applicable) and JNJ-3989 at Week 4 (or 8) as reference. The primary PK parameters are C_{max} and AUC_{24h} on the logarithmic scale. A mixed effects model will be fitted to log-transformed PK parameters with treatment period as a fixed effect and participant as a random effect.

Special attention will be paid to the plasma concentrations and PK parameters of those participants who discontinued the study for an AE, or who experienced an AE \geq grade 3, or an SAE.

Population PK analysis of plasma concentration-time data of JNJ-3976 and JNJ-3924 may be performed using non-linear mixed effects modeling. Data may be combined with those from Phase 1 and/or 2 studies to support a relevant structural model. Available baseline characteristics (eg, demographics, laboratory variables, genotypes) may be included in the model as necessary. If a population PK analysis is conducted, the results will be presented either in the clinical study report or in a separate report.

Pharmacokinetic/Pharmacodynamic Analyses

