
 To evaluate the efficacy of the study intervention during the FU period. 	
 Proportion of participants with HBsAg seroclearance at Week 48 (ie, 24 weeks after completion of all study interventions at Week 24) without re-starting NA treatment. Proportion of participants with HBV DNA <LLOQ at Week 48 (ie, 24 weeks after completion of all study interventions at Week 24) without re-starting NA treatment. Frequency of virologic and/or biochemical flares. Proportion of participants requiring NA re-treatment.

 To evaluate the pharmacokinetics (PK) of JNJ-3989 (JNJ-3924 and JNJ-3976), and optionally of JNJ-6379, NA and PegIFN-α2a. 	
 PK parameters of JNJ-3989 (JNJ-3924 and JNJ-3976). Optionally, PK parameters of JNJ-6379, NA and/or PegIFN-α2a compared to historical data.
Exploratory	

 To explore host and viral baseline and on-treatment markers associated with end of treatment and/or off-treatment response. 	
 Association of baseline characteristics and baseline/on-treatment host and viral blood markers (such as age and HBsAg levels) with selected on or off-treatment efficacy variables.

 To explore changes in the severity of liver disease. 	
 Changes in fibrosis (accounting to Fibroscan liver stiffness measurements) at EOSI and the end of the FU period versus baseline.

 To explore efficacy of the study intervention in terms of changes in HBV RNA and hepatitis B core-related antigen (HBcrAg) levels during the study intervention and FU period. 	
 Changes from baseline in HBV RNA and HBcrAg levels over time.

 To explore the relationship of PK with selected pharmacodynamic (PD) parameters of efficacy and safety. 	
 Relationship of various PK parameters with selected efficacy and safety endpoints.

 To explore the effect of PegIFN-α2a coadministration on the PK of JNJ-3989 (JNJ-3924 and JNJ-3976) and JNJ-6379^c, as applicable (PK substudy). 	
 Effect of PegIFN-α2a coadministration on the PK of JNJ-3989 (JNJ-3924 and JNJ-3976) and JNJ-6379, as applicable.

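### The model for the PegIFN effect on JNJ-3989 PK has no JNJ-6379 term, so any effect of stopping JNJ-6379 between the two profiles would be read as a PegIFN effect

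*SAP*

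**What the plan says.** The exploratory objective in SAP 1.1 begins "To explore the effect of PegIFN-α2a coadministration on the PK of JNJ-3989". It is addressed in the optional intensive-PK substudy. The test profile is taken with PegIFN at Week 20 (or 16), and each analyte's profile "at Week 4 (or 8) as reference" is the comparator. SAP 5.7.1 states that a mixed effects model "will be fitted to log-transformed PK parameters with treatment period as a fixed effect and participant as a random effect". Protocol 9.4.4 words the model identically. Neither text has a term, restriction or stratum for JNJ-6379 use.

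Protocol 4.2 describes the urgent stop under Amendment 3: "Participants currently on treatment with JNJ-6379 were contacted and requested to stop taking JNJ-6379", while NA, JNJ-3989 and PegIFN continued. SAP 5.1.10 recognises the consequence. Its Group 2 took no JNJ-6379 in Treatment Period 2, but may have had it in Treatment Period 1. Group 1 needs only a single JNJ-6379 tablet in Period 2. SAP 5.1.10 allows some analyses by these groups without saying which. SAP section 1 leaves PK details to a separate analysis and modeling plan, which is not among the documents.

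**The concern.** A within-participant comparison isolates PegIFN only if the rest of the regimen is the same at both profiles. That was true of the design before Amendment 3. It is not true for a participant who was on JNJ-3989 + JNJ-6379 + NA at Week 4 or 8 and on JNJ-3989 + NA + PegIFN at Week 16 or 20, because two drugs change at once. With period as the only fixed effect, the model cannot say which of them moved JNJ-3989 exposure. A real JNJ-6379 effect would be reported as a PegIFN interaction, or could mask one.

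A smaller related point concerns NA. SAP 1.1 lists, as an option, comparison with historical data: "Optionally, PK parameters of JNJ-6379, NA and/or" PegIFN. Protocol 2.2.3.2 reports higher tenofovir troughs when tenofovir disoproxil is given with JNJ-6379, so such a comparison would need to separate participants by JNJ-6379 use.

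**Working it through.** The documents state no sample size, variability or expected effect for this comparison, so there is no planned figure to reproduce. The check is algebraic.

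**Inputs**
- Model and visits: SAP 5.7.1 and Protocol 9.4.4.
- Regimen change between the periods: SAP 5.1.10 and Protocol 4.2.
- s, the share of paired profiles with JNJ-6379 at the reference only: not given; 25 to 75% is assumed, and zero is possible.
- R, the factor by which JNJ-6379 multiplies JNJ-3989 exposure: no human value is given; 0.80 to 1.25 is assumed.

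**Derivation.** With one reference and one test profile per participant, the period coefficient is the mean within-participant log difference. Let P be the true PegIFN ratio.
- Same JNJ-6379 status at both profiles: expected difference = log(P).
- JNJ-6379 at the reference only: expected difference = log(P) − log(R).
- Average: log(P) − s·log(R), so the apparent ratio is P × R^(−s).

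**Result with P = 1.00**

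| R | s = 25% | s = 50% | s = 75% |
|---|---|---|---|
| 1.25 | 0.95 | 0.89 | 0.85 |
| 1.00 | 1.00 | 1.00 | 1.00 |
| 0.80 | 1.06 | 1.12 | 1.18 |

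For example, 1.25^(−0.75) = 0.846 and 0.80^(−0.75) = 1.182.

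**Simulation of the stated model.** Assumptions: 12 participants, log-scale SD 0.3 between and 0.2 within participants, 300 data sets, P = 1.00, R = 0.80, all other participants off JNJ-6379 at both profiles. The apparent ratio was 1.054 at s = 25%, 1.123 at 50% and 1.241 at 100%. The algebra gives 1.057, 1.118 and 1.250.

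**With a visit-level JNJ-6379 term.** The ratio returned to 0.996 (s = 25%) and 1.004 (s = 50%). The empirical standard error on the log scale rose from 0.080 to 0.094 and from 0.086 to 0.113. At s = 100% the two effects cannot be separated.

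**Residual exposure.** Protocol 2.2.3.1 gives mean single-dose terminal half-lives of 93.3 to 110.5 hours for 25 to 300 mg of JNJ-6379, and 141.3 hours for 600 mg. Assuming simple exponential decline, the fraction left one week (168 hours) after the last dose is 2^(−168/93.3) = 0.29 to 2^(−168/141.3) = 0.44. Intake on the sampling day is therefore a poor measure of exposure for someone who stopped recently.

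**Tenofovir.** Protocol 2.2.3.2 gives Week 12 troughs of "94.2 [30.0] and 115 [66.0] ng/mL for 75- and 250-mg JNJ-6379" with tenofovir disoproxil, against 66.8 ng/mL for tenofovir disoproxil without JNJ-6379. The ratio at 250 mg is 115/66.8 = 1.72.

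**The case against.** The strongest reply is that there may be nothing to confound. The bias is zero if JNJ-6379 does not change JNJ-3989 exposure. Protocol 2.2.2.1 reports no relevant interaction in the 1-month rat combination study and none in the 3-month study, and Protocol 2.2.3.2 repeats this. Uptake of the substudy is not given, so there may be few affected pairs or none. This stands: it limits the size of the problem, though rat data do not settle the question in people.

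A second reply is that the separate PK plan, or the by-group analyses in SAP 5.1.10, may deal with it. The separate plan may. The groups would not do so fully even if applied, because a Group 1 member can have stopped JNJ-6379 before Week 16 or 20. The qualifier that JNJ-6379 is included as applicable governs only whether its own PK is compared; it does not alter the JNJ-3989 model.

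Three stronger readings are tempting, and the documents do not support them:
- A reader might infer that participants who never received PegIFN count as PegIFN-exposed, since SAP 5.1.1 gives them a Treatment Period 2. Both documents define the test profile as one coadministered with PegIFN, so such profiles are already outside the comparison.
- A reader might infer a biased tenofovir comparison between Week 20 and Week 4, or NA profiles pooled across JNJ-6379 use. The mixed model covers JNJ-3989 and, as applicable, JNJ-6379. NA bioanalysis is optional, and no text says that NA profiles will be pooled.
- A reader might take the suspected negative effect of JNJ-6379 on HBsAg lowering (Protocol 2.2.3.1) as evidence of altered JNJ-3989 exposure. That observation concerns HBsAg, not concentrations.

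**Conclusion.** The structural point holds. As written, the model cannot separate starting PegIFN from stopping JNJ-6379 in participants who had JNJ-6379 at the reference profile only. These are part of Group 2 and possibly some of Group 1. Participants with the same status at both profiles are unaffected.

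It does not follow that the JNJ-3989 estimate is biased. The bias is −s·log(R), with both quantities undocumented, and the available nonclinical evidence points to a small or zero value. The range of 0.85 to 1.18 illustrates assumed inputs and is not a forecast. The comparison is exploratory, in an optional substudy, with no formal test (SAP 5.1.7), and does not touch the primary endpoint. Severity: minor.

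**What to change.** In SAP 5.7.1 and Protocol 9.4.4, or by explicit reference to the separate PK plan if it already does this:

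1. Add a visit-level JNJ-6379 exposure term to the JNJ-3989 model. Derive it from dosing dates and allow for residual exposure after the last dose in view of the long half-life.
2. Also report the paired estimate in participants with the same JNJ-6379 status at both profiles, using only test profiles actually taken with PegIFN.
3. Report how many pairs changed status. If all did, state that the two effects cannot be separated.
4. If NA PK is compared with historical data, present tenofovir disoproxil recipients by JNJ-6379 status at sampling.

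The JNJ-6379 start and end dates are already used for exposure and compliance (SAP 5.6.1 and 6.7), so no new data are needed. The cost is precision. In the simulation the standard error rose by a factor of 0.094/0.080 = 1.18 at s = 25% and 0.113/0.086 = 1.31 at s = 50%. The loss grows with s, and the same-status set is smaller than the full substudy.
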